Hypothesis: Gait analysis and Postural analysis will accurately capture changes in gait and postural stability associated with OH treatment, with higher sensitivity and lower variability than standard clinical tests.

Aim #2 To evaluate the feasibility and calculate the effect size of using WMS to quantify OH related postural instability during at-home activities of daily living

Gait and postural stability will be evaluated in the home environment by means of the following outcome measures:

Clinical assessment: Self-assessed clinical diary (OHDAS-based score) evaluating the subjective sensation of postural instability and number of episodes of postural instability.

WMS assessment: WMS (Apple Watch®) evaluating functional parameters, namely a) number of steps per day; b) number of hours of standing per day; c) total calories and active calories per day.

Hypothesis: TOMs will provide an accurate measure of functional parameters in the home setting, thus allowing an indirect measure of the patients' quality of life, with higher sensitivity and lower variability than self-reported clinical diaries.

INVESTIGATOR EXPERIENCE: Please see attached Bio sketch.

CLINICAL EVALUATIONS

Screening Assessment (Day 0)

12 consecutively consenting PD patients with OH about to start pharmacological treatment with a vasopressor agent (Droxidopa), as prescribed by their treating physician from the Gardner Family Center for Parkinson's Disease and Movement Disorders, will be screened for the following inclusion/exclusion criteria:

Inclusion criteria: (a) Diagnosis of idiopathic PD, meeting UK Brain Bank criteria [15] for at least 3 years; (b) Hoehn and Yahr (H&Y) stage I-III; (c) Age between 30 and 80 years old (both inclusive); (d) Stable dosage of dopaminergic medications for at least 4 weeks; (e) OH, defined as a fall in systolic BP \geq 20 mmHg or diastolic BP \geq 10 mmHg within 3 minutes of standing [16]; (f) Willingness and ability to comply with scheduled visits.

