Clinical Assessments: Motor severity as per the MDS-Unified Parkinson's Disease Rating Scale (MDS UPDRS) [20]; OH symptoms severity as per the full OHQ (OHSA and OHDAS) scale [7]; quality of life as per the PD questionnaire (PDQ-39) [11]; Cognitive assessment as per the Cambridge automated neuropsychological test battery (CANTAB) [12] and CERAD-NAB [13].

Clinical Diary: Patient will be instructed to score the severity of the OH-related episodes of postural instability and the number of episodes of postural instability a day before starting titration with droxidopa, 1 day after V2 and 1 day after V3; using a self-assessed clinical diary based on the OHDAS (a section of the OHQ assessing the impact of OH symptoms on standing and walking).

Gait Assessments (average of two measurements): In order to evaluate variables of interest (stride length, single leg stance time, dynamic stability index, and gait velocity), patients will be assessed walking on the 20 feet-Protokinetics Zeno Walkway. Patients will be instructed to "walk from the mark (red tape) before the mat to the mark after the mat, turn around and walk back". After a preliminary review for acquisition errors, the data will downloaded into a Matlab-based software platform prepared ad-hoc for this study (Matlab, Mathworks, CA, USA) by the Department of Bioengineering of the University of Cincinnati ([name]).

Postural Assessments (average of two measurements): In order to evaluate variables of interest (postural sway on the X and Y-axis, as measured by the center of mass estimated X and Y range), patients will be asked to perform a modified Clinical Test of Sensory Interaction on Balance. Patients will stand on the mat for 30 seconds under the 2 following conditions: eyes open/rest and eyes closed/rest, with their feet 1"-2" apart and arms at their side. For the eyes open condition, he/she will be asked to focus on a point in front of him/her at eye level to control for visual distractions. Data will be collected and stored into the software platform described above.

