WMS Assessment: Patients will be provided an Apple Watch® with dedicated app (e.g., the Activity app®), able to measure number of hours of standing per day, and total calories and active calories per day. The Apple Watch® will be connected with an iPhone and will be given to each subject together with dedicated instructions to fill out the OH-related diary. More in details, patients will be instructed to charge the Apple Watch® and the iPhone® every night before going to bed, and to wear the watch the day after when they wake up. Total number of hours in which the patients will wear the watch will be counted at the end of the study, based on the data provided by the Apple Watch®. Data collected by the Apple Watch® will be downloaded after the end of the study and will provide information related to number of steps per day, number of hours of standing per day, and total calories and active calories per day.

Droxidopa Titration Plan

Droxidopa will be started after 2 days of baseline data collection at the dosage of 100 mg 3 times a day (TID). Dose-optimization will be titrated over a 2-week period in 100- mg TID increments every 2 days until at least one of the following criteria is met:

- Self-rating score of 0 at the item 1 of the OHQ, plus an increase in standing systolic BP ≥ 10 mm Hg, compared with the baseline value, as measured 3 minutes post-standing (and 3 hours after a Droxidopa dose).
- Reaching the maximum permitted dosage of 600 mg TID.
- Sustained BP > 180 mmHg systolic or > 110 mmHg diastolic while standing, sitting, or supine.

Visit 2: Patients will receive a complete BP assessment following the same procedure detailed in Visit 1 (see above), and a standard neurological examination. Adverse events and side effects associated with Droxidopa treatment will also be addressed, adjusting the dosage of Droxidopa if needed. Technical issues related to the use of Apple Watch® will also be discussed, if present.

Visit 3: This evaluation will be performed in the morning, at 8:00 AM before breakfast and at least 1 hour after the first dose of dopaminergic medications, 4 weeks after Visit 2. Patients will undergo a complete clinical, gait, postural and BP assessment, as per the protocol described in Visit 1.

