Data will be described with appropriate summary measures (mean and SD, or median and interquartile range) at Visit 1 (before Droxidopa treatment) and Visit 3 (after 4 weeks of Droxidopa maintenance therapy). Changes in the main clinical (PDQ-39, Tinetti, OHQ and related subscales), gait (stride length, single leg stance time, dynamic stability index, and gait velocity) and postural (postural sway on the X and Y axis) outcomes will be compared between Visit 1 and Visit 3 using the paired t-test/ non parametric Wilcoxon signed rank test depending on the distribution of change outcome. Effect size (mean or median change and percent change) will be reported along with 95% confidence interval (CI). In addition, data collected with TOMs before and after treatment with Droxidopa will be correlated with changes in the PDQ-39, OHQ, CANTAB and CERAD-NAB by means of the Pearson correlation/Spearman rank correlation analysis.

Hypothesis: Gait analysis and Postural analysis will accurately capture changes in gait and postural stability associated with OH treatment, with higher sensitivity and lower variability than standard clinical tests.

Aim #2 To evaluate the feasibility and calculate the effect size of using WMS to quantify OH related functional parameters during at-home activities of daily living

Postural data collected from WMS (Apple Watch®) and evaluating: (1) Number of steps per day; (2) number of hours of standing per day; and (3) total calories and active calories per day, will be analyzed and compared with episodes of subjective (OHDAS-based diary) postural instability recorded during the follow-up period using a paired t-test/Wilcoxon signed rank test. In addition, we would also evaluate the changes from pre-baseline to post baseline of subjective measure of postural stability and correlate with objective measures of postural stability using Pearson correlation/Spearman rank correlation analysis. Statistical analyses will be carried out using SAS 9.3.

Hypothesis: WMS will provide an accurate measure of functional parameters in the home setting, thus allowing an indirect measure of the patients' quality of life, with higher sensitivity and lower variability than self-reported clinical diaries.

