Missing data on the scores will be handled by a two-step approach. Less than 20% missing data on any variable for an individual will be imputed using the mean of the final score of that question. Greater than 20% missing data for any participant on any instrument will be handled by a multiple missing imputation approach. Missing data on BP related variables will be imputed using multiple missing imputation approach.

Sample Size Calculation: Given the exploratory nature of this pilot study, the sample size calculation is inevitably limited by the lack of previous data. We used a study analyzing the effect of levodopa in PD with

a gait analysis [21], which reported a 30% improvement in the stride length (SD 31.3%), to pre-specify a threshold of minimal improvement of 10% between baseline and follow-up. With these assumptions, we estimate that a sample of 12 patients will be more than sufficient to detect significant differences using a paired t-test, with more than 80% power and at 5% level of significance (PASS 14 Power Analysis and Sample Size Software (2015). NCSS, LLC. Kaysville, Utah, USA, ncss.com/software/pass).

Innovation

Although TOMs are unanimously thought to represent the future of medical assessments, their routine application is limited by the lack of validation studies proving their efficacy and reliability in clinical trials. The current proposal will provide more sensitive standards for the assessment of OH complications in PD, with the main innovation of developing and validating an innovative outcome measure based on a mobile (WMS) and in-clinic (gait analysis) technology.

DATA STORAGE AND CONFIDENTIALITY:

All records from this study will be maintained in a secure setting. We will be using REDCap (Research Electronic Data Capture) as the secure web-based application to store data for this research study. Records will not have any patient health information (PHI) associated with them. These records will be kept indefinitely to allow for re-analysis of data, if needed. The data will never be accessible without a secure password.

RISKS AND BENEFITS:

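### Aim 2 and the Innovation section claim that the watch is accurate and validated, but no planned analysis compares a watch variable with a reference for the same quantity

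*Combined protocol and SAP*

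**What the plan says.** The claim appears in three places in the combined protocol and SAP. Under Aims of the Study, Aim #2, the hypothesis is that "TOMs will provide an accurate measure of functional parameters in the home setting". Under Data Analysis, Aim #2, the same sentence is written for the watch: "WMS will provide an accurate measure of functional parameters in the home setting". The Innovation section describes the main innovation as "developing and validating an innovative outcome measure based on a mobile (WMS) and in-clinic (gait analysis) technology".

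The aim itself is more modest. Data Analysis gives it as "To evaluate the feasibility and calculate the effect size of using WMS to quantify OH related functional parameters during at-home activities of daily living".

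The WMS Assessment section lists the watch output as "number of steps per day, number of hours of standing per day, and total calories and active calories per day". In the Aim 2 analysis these variables are to be "compared with episodes of subjective (OHDAS-based diary) postural instability recorded during the follow-up period using a paired t-test/Wilcoxon signed rank test". The Aims section describes the diary as "evaluating the subjective sensation of postural instability and number of episodes of postural instability". The Aim 2 analysis adds a correlation between change in subjective stability and the objective measures. The Aim 1 analysis correlates technology-based measures with PDQ-39, OHQ, CANTAB and CERAD-NAB, without saying whether the watch is included.

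**The concern.** Accuracy means agreement with a reference for the same quantity in the same units. Association with a different quantity does not show it. As written, the hypothesis has no planned analysis that could refute it: the plan could be followed exactly and a badly calibrated watch would go unnoticed.

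What is at stake is the wording of the conclusion and its later use. The Future Directions section says the data will inform a larger proposal, and the Experimental Design section foresees these measures being used in place of subjective scales. A reader of the final report could take the watch as validated when it had never been checked.

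Measurement error could also reach the effect size, but only if it changes between visits. A constant proportional miscount cancels from a within-patient percent change. A miscount that shifts with gait does not, and gait is what treatment is expected to change.

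**Working it through.** **Design figure in the plan.** The only one is in Sample Size Calculation: 12 patients, paired t-test, 5% level, more than 80% power, based on a 30% stride-length improvement with SD 31.3%. With noncentrality (30/31.3) × √12 = 3.32 and 11 degrees of freedom, exact two-sided power is 85.5%, so the figure reproduces on the 30% input. It concerns stride length. The documents give no figure for watch accuracy or agreement.

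**Planned uses of the watch variables.**

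| Planned analysis | Comparator | Measures steps, standing hours or calories? |
|---|---|---|
| Paired t-test or Wilcoxon (Aim 2) | Diary episodes of instability | No |
| Correlation (Aim 2) | Change in subjective stability | No |
| Correlation (Aim 1, if the watch is included) | PDQ-39, OHQ, CANTAB, CERAD-NAB | No |

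The walkway is used for stride length, single leg stance time, dynamic stability index, velocity and sway. It is not planned as a reference for the watch. No observed count, second monitor, agreement statistic or acceptance limit appears.

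**Could these tests reveal an inaccurate watch?**

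- Correlation: for any constant c > 0, corr(c × watch, diary) = corr(watch, diary). Illustration: 20,000 simulated samples of 12 patients, with assumed mean 4,000 and SD 1,500 steps per day and an assumed diary score equal to −0.6 × standardised steps plus noise of SD 0.8. The mean correlation is −0.58 for a perfect watch and −0.58 for one recording 60% of steps.
- Paired t-test of steps against diary episodes (3 episodes assumed): noncentrality is (4,000 − 3)/1,500 × √12 = 9.23 for the perfect watch and (2,400 − 3)/900 × √12 = 9.23 for the one missing 40%. Power is near 100% in both cases. The test rejects because the units differ, whatever the accuracy.

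**When would miscounting distort the effect size?** Suppose true steps do not change and the proportion detected is 70% before treatment (assumed). If it stays at 70%, the percent change is 0. If it rises to 75% or 85%, the watch shows 75/70 − 1 = 7% or 85/70 − 1 = 21% false gain.

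**What could 12 patients show if a reference were added?** With one paired difference per patient and t(0.975, 11) = 2.201:

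- Mean bias: 2.201/√12 = ±0.64 SD of the differences.
- Each limit of agreement: 2.201 × √(1/12 + 1.96²/22) = ±1.12 SD.

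The documents give no SD for such differences, so these stay in SD units. For the planned correlations, |r| must reach about 0.58 for two-sided p < 0.05, and an observed r of 0.80 has a 95% interval of 0.42 to 0.94.

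**The case against.** The strongest reply is that accuracy is not what the study sets out to estimate. The title and both statements of Aim 2 speak of feasibility and effect size. There is no accuracy endpoint or decision rule, and the Innovation section is not an analysis section. The hypothesis sentence also goes on to sensitivity and variability relative to diaries, which is a separate comparison. This stands as a limit on the point: the missing reference does not block the stated aim. It does not rescue the claim, because a stated hypothesis needs an analysis able to contradict it.

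Second, a reader might infer that no form of validation is possible. That goes too far. The planned correlations with the diary and questionnaires could give weak convergent evidence. Only accuracy and criterion (agreement) validity are ruled out.

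Third, a reader might infer that wrist counts are wrong in these patients, or that the larger trial will adopt the watch regardless. The documents support neither. They say nothing about tremor, arm swing or walking aids affecting the watch, they exclude severe functional impact of dyskinesia, and they say only that the data will inform a later proposal.

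Fourth, it is tempting to call the walkway a ready-made, nearly free reference, since "patients will be assessed walking on the 20 feet-Protokinetics Zeno Walkway" at Visits 1 and 3. The Gait Assessments section does not bear this out. Patients start at a mark before the mat, finish beyond it, turn and walk back, so the watch may count steps that the mat cannot. A pass over 6.096 m at an assumed 0.4 to 0.7 m per step is 15.2 to 8.7 steps. An assumed 2 to 4 off-mat steps per pass would then create an artefact of 2/15.2 = 13% to 4/8.7 = 46%. No walkway step count is listed, and watch output is described only as daily totals.

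**Conclusion.** The accuracy and validation wording for the watch is not supported by the design. None of the four watch variables is compared with a reference for the same quantity, and the planned tests would give the same answer for a perfect watch and for one missing 40% of steps. This conclusion rests on reading the documents. The simulation and the detection rates are illustrations on assumed values, and the size of any real watch error is unknown.

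The study can still report feasibility, effect size and weak convergent association. The defect therefore lies in what may be concluded about the watch, and it does not defeat Aim 2.

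**What to change.** Reword the Aim 2 hypothesis in both the Aims and the Data Analysis sections, and the watch part of the Innovation section. Replace *accurate* and *validating* with feasibility, effect size (change from baseline with 95% CI) and association with the diary and questionnaires. Add one sentence stating that the study cannot support a conclusion on watch accuracy. The cost is a narrower claim.

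Optionally, and only if short-interval watch step counts can be exported, add a descriptive check:

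- Patients wear the watch during the existing walkway walks at Visits 1 and 3. At Visit 1 this means issuing it before the gait test, an order the protocol does not state.
- The reference is an observed step count over the whole mark-to-mark walk including the turn, not the on-mat count. The Risks and Benefits section already has a researcher walking beside the patient.
- Take one watch-minus-observed difference per patient at each visit, and report the mean difference and limits of agreement with their intervals.
- Restrict any statement to step count during in-clinic walking.

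This costs an export check, an observed count at two existing visits and one table. Precision will be coarse, and short clinic walks say nothing about standing hours, calories or accuracy at home.

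### The claimed power of over 80% does not hold for the pre-specified 10% improvement in stride length: 12 patients give about 17%

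*Combined protocol and SAP*

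**What the plan says.** The Sample Size Calculation, at the end of the Data Analysis section, relies on one earlier gait study of levodopa, "which reported a 30% improvement in the stride length (SD 31.3%), to pre-specify a threshold of minimal improvement of 10% between baseline and follow-up". The next sentence refers back to those inputs as its assumptions and estimates that "a sample of 12 patients will be more than sufficient to detect significant differences using a paired t-test, with more than 80% power", tested "at 5% level of significance". PASS 14 is named as the software.

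The paragraph does not say whether the test is one- or two-sided. It gives no within-patient correlation, no separate SD for the paired difference and no allowance for dropout. It also admits that the calculation is limited because earlier data are lacking. Under Aim 1, stride length is one of the gait outcomes compared between Visit 1 and Visit 3 by paired t-test or Wilcoxon signed rank test, with effect sizes and 95% confidence intervals reported.

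**The concern.** The only effect the plan pre-specifies is 10%, and the power statement follows directly from it. A 10% change against an SD of 31.3% is a standardised effect of about 0.32. Twelve pairs cannot detect an effect that small with 80% power.

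This paragraph is the study's only justification for its sample size. The study's hypothesis is that gait and postural analysis capture treatment change with greater sensitivity than clinical scales, and the Future Directions section says the results will inform a larger proposal. A reader who believes the study had over 80% power for a 10% improvement could take a non-significant stride-length result as evidence that the gait measure failed, or that no such improvement exists. With the stated inputs, such a result would be expected most of the time even if the improvement were real.

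**Working it through.** **Inputs, all from the Sample Size Calculation**

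- n = 12 pairs; paired t-test; 5% significance level.
- Pre-specified improvement: 10%. Improvement in the cited study: 30%.
- SD = 31.3%, read as the SD of the within-patient percent change (assumption).
- Two-sided test (assumption; one-sided shown as well).

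**Formula.** Power comes from the non-central t distribution with n − 1 = 11 degrees of freedom and non-centrality λ = (improvement / SD) × √n. The two-sided critical value is 2.201.

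**Step 1: look for the plan's own figure**

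| True improvement | Standardised effect | λ | Power, two-sided | Power, one-sided | n for 80%, two-sided |
|---|---|---|---|---|---|
| 10% (the stated threshold) | 10/31.3 = 0.319 | 1.107 | 17.3% | 27.2% | 79 |
| 20% (a true 30% tested against 10%) | 20/31.3 = 0.639 | 2.213 | 52.4% | 66.6% | 22 |
| 30% (the cited levodopa response) | 30/31.3 = 0.958 | 3.320 | 85.5% | 92.8% | 11 |

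Only the 30% row gives power above 80%. A normal approximation at 10% gives 19.7%, so the choice of method does not explain the gap. One-sided, 62 patients would be needed for 10%.

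**Step 2: what 12 patients can detect**

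- Standardised effect for 80% power, two-sided: 0.889. Detectable improvement = 0.889 × 31.3 = 27.8% (24.0% one-sided).
- SD of change at which 10% would have 80% power: 10 / 0.889 = 11.25%.
- Expected 95% CI half-width = 2.201 × 31.3 / √12 = 19.9 percentage points.

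**Step 3: 31.3% as the SD at each visit.** The SD of the difference is then 31.3 × √(2(1 − ρ)), where ρ is the within-patient correlation.

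| ρ | SD of difference | Power at 10%, two-sided |
|---|---|---|
| 0 | 44.3 | 11.1% |
| 0.5 | 31.3 | 17.3% |
| 0.7 | 24.2 | 25.7% |
| 0.8 | 19.8 | 35.9% |
| 0.9 | 14.0 | 61.6% |

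For 80% power, ρ = 1 − (11.25 / 31.3)² / 2 = 0.935. The documents give no correlation.

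**Step 4: margin if 30% was the planning effect.** Power is 85.5% with 12 completers, 81.7% with 11 and 77.0% with 10. By simulation under normal changes, the Wilcoxon alternative with 12 patients has about 82% power at 30% and 15% at 10%.

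**The case against.** The arithmetic at 10% is not in dispute. The best case for the plan has three parts.

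**The figure was probably computed for 30%.** The paragraph does not say which effect was entered in the software, and 30% with SD 31.3% gives 85.5%. The defect may therefore be a 10% threshold attached to a calculation made for 30%. This is the likely origin, but the text names 10% as the minimal improvement, never says that the power refers to 30%, and links the claim to the assumptions just stated. A reader would take it as power for 10%.

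**The meaning of 31.3% cannot be verified.** The cited study is not available here. The in-text citation is number 21, which in the reference list is the MDS-UPDRS paper; the levodopa gait study is number 22. If 31.3% were relative to the 30% improvement, the SD would be 0.313 × 30 = 9.4 points and power at 10% would be 91.8%. That is a strained reading of an improvement followed by its SD, and nothing in the documents supports it. It does mean that the SD has to be labelled as an assumption.

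**This is an exploratory feasibility and effect-size study.** No go/no-go rule depends on significance for stride length, confidence intervals are already planned, and the likely misreading of a null result is a prediction, not something the plan says. This limits the consequence and supports leaving the sample size alone. It does not make the stated power correct: a pilot need not have 80% power, but a plan that claims it should have it under its own inputs.

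**Conclusion.** The concern holds. As written, the plan claims over 80% power where its own inputs give 17.3% two-sided, or 27.2% one-sided. A true 10% improvement would be missed about five times in six (1 − 0.173 = 0.827).

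The result rests on 31.3% being the SD of the within-patient change, on 12 evaluable patients and, for the headline figure, on a two-sided test. Changing the sidedness does not rescue the claim. Reading 31.3% as a per-visit SD would rescue it only with an unstated correlation of about 0.935. The claim is supportable for a 30% improvement, with a narrow margin for loss of patients.

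**What to change.** Keep 12 patients and correct the statement. Suggested text:

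> Assuming that 31.3% is the SD of the within-patient percent change in stride length and that all 12 patients are evaluable, a two-sided 5% paired t-test has about 86% power for a 30% improvement and about 17% for a 10% improvement. The smallest improvement detectable with 80% power is about 28%, and the expected 95% confidence-interval half-width is about 20 percentage points. A non-significant result does not exclude a 10% improvement; conclusions will rest on the confidence interval.

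Remove the assertion that 12 patients more than suffice. Confirm from the cited study what the 31.3% describes, and correct the citation number. If the SD proves to be something else, or a one-sided test was intended, recompute the figures on that basis and say so.

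The cost is protocol wording only: no extra patients, visits or analyses, since the confidence intervals are already planned. The stated power becomes less favourable.
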